### 9.3.3 Covariates

Covariates such as demographics (sex, race, geographical region, age), baseline medical conditions (renal function, hypertension, diabetes, peripheral arterial occlusive disease, diabetic foot, coronary artery disease, diabetic neuropathy, diabetic retinopathy, history of lower-limb amputation, osteomyelitis, gangrene, nephropathy, HF at baseline, smoking

Proprietary confidential information © 2019 Boehringer Ingelheim International GmbH or one or more of its affiliated companies

status; for patients with diabetes: HbA1c), and baseline therapies (diuretics, loop diuretics, anticoagulants, anti-platelets; for patients with diabetes: insulin, metformin, sulphonyl urea) will be investigated in subgroup analyses of the LLA events and AEs related to amputation.

In addition, further demographic and baseline variables will be descriptively summarised (i.e. ethnicity, BMI, weight, time since diagnosis of diabetes, blood pressure).

All demographic and baseline variables with categories are shown in Table 9.3.3: 1 (also see the SAP [[c16853237](#), Table 4.3: 2]).

Table 9.3.3: 1 Demographic and baseline variables with categories

Variable	Demographics/Baseline characteristics Categories
Sex	Male Female
Race	White Black/African Asian Hawaiian/Pacific Islander Amer. Ind./ Alaska Nat.
Ethnicity	Hispanic/Latino Not Hispanic/Latino
Geographical region &	Europe Africa/Middle East North America Latin America Asia Other (if any)
Age (years) categories	Version 1 <65 65 to <75 75 to <85 ≥85  Version 2 <65 65 to <75 ≥75
	(Decision will be taken on which version to use based on the size of the elderly population group ≥85 years of age)
BMI (kg/m  )	<25 25 to <30 30 to <35 ≥35
Weight (kg)	≤70 >70 to ≤80 >80 to ≤90 >90

To be continued

Table 9.3.3: 1 Demographic and baseline variables with categories (continued)

Variable	Demographics/Baseline characteristics	
	Categories	
Smoking status	Never smoked	
	Ex-smoker	
	Currently smokes	
Time since diagnosis of diabetes	Version 1 for SAF-M1 pool: ≤1 year >1 year to 5 years >5 years to 10 years >10 years Not applicable (as no diabetes diagnosed)	Version 2 for SAF-M2 pool: ≤1 year >1 year to 5 years >5 years to 10 years >10 years to 20 years >20 years Not applicable (as no diabetes diagnosed)
Baseline HbA 1c (%)	Version 1 <8.5 ≥8.5	Version 2 <8 8 to <9 (for diabetic patients only)
Blood pressure (mmHg)	≥130/80 <130/80 (controlled)*	

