## **9.7 DATA ANALYSIS**

This meta-analysis will be exploratory. For the primary outcome of LLA events and for the secondary outcome of AEs related to amputation, a Cox proportional hazards regression model for modelling the time to first event will be used, including the factors study, diabetes mellitus status (T1DM, T2DM, no diabetes), and treatment (all empa vs. placebo). Study is assumed as fixed effect in this meta-analysis. For treatment comparison, hazard ratios with corresponding 95% CIs as well as corresponding p-values will be presented (see the SAP [[c16853237](#), Section 4.3]).

All analyses will be based on the treated set, which includes all patients treated with at least 1 dose of study medication (as randomised). Due to the different patient eligibility criteria (see [Section 9.2.2](#)) and methods in capturing LLA and related events (see [Section 9.3.2.1](#)), two analysis groupings will be used in the meta-analysis. SAF-M1 includes all 3 studies while SAF-M2 includes studies 1245.110 and 1245.121 (Table 9.7: 1; also see the SAP [[c16853237](#), Table 3.1.2: 1]). All analyses will be carried out separately for each SAF and for each study, unless otherwise indicated in [Table 9.7: 2](#).

Table 9.7: 1 Overview of analysis groupings and individual studies

Grouping	Description	Studies	Purpose
SAF-M1	All studies	1245.25	Frequencies, incidence rates and time to onset of amputation events
		1245.110 1245.121	Frequencies, incidence rates and time to onset for related events based on selected adverse events
SAF-M2	Chronic heart failure studies	1245.110	Frequencies, incidence rates and time to onset of amputation events
		1245.121	Frequencies, incidence rates and time to onset for related events based on selected adverse events
			Details on lower limb amputations

The results of the meta-analysis will be presented mainly in tabular form, and when appropriate, in graphical form.

Tabulations of frequencies for categorical data will include all different categories and display the number of observations and the percentage (%) in a category relative to the respective treatment group (placebo, empa 10 mg, 25 mg, all empa). The category "missing" will be displayed if there are actually missing values. Percentages will be based on all patients in the respective patient set whether they have non-missing values or not.

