### **9.7.1 Main analysis**

LLA events (primary outcome) and AEs related to amputation (secondary outcome) will be analysed using frequency analyses, incidence rates, Kaplan-Meier estimates, and Cox proportional hazards models to compare empagliflozin with placebo in the pooled populations of SAF-M1, SAF-M2, and for each of the 3 studies (1245.25, 1245.110, and 1245.121) separately. Kaplan-Meier analyses (cumulative incidence functions) for time to first event will be provided by treatment and stratified by study.

Cox proportional hazards models will include the factors study, diabetes mellitus status (T1DM, T2DM, no diabetes), and treatment (all empa vs placebo).

As the primary analysis, the “on-treatment” approach will include events with an onset date within the treatment period (from first to last dose of study medication plus 7 days to account for the residual drug effect).

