#### 9.7.2.3 Subgroup analysis

All subgroup variables with categories are shown in [Table 9.3.3: 2](#). Subgroup analyses for SAF-M1 and SAF-M2 will be provided for frequency and incidence rate tables, KM analyses, and for Cox models. Subgroup analyses will be performed for LLA events and AEs related to amputation.

For Cox models for time to first event analysis, the following factors will be included in the model: study, treatment, <subgroup>, treatment-by-<subgroup> interaction.

For time-to-event endpoints, at a minimum, a count of events will be provided, and if sample size is statistically sufficient, i.e. 14 patients with events in total over the 2 treatment groups for each subgroup category, a statistical analysis using the Cox regression model will be performed. If the affected category is too small (<14 patients with events), the category may be only described descriptively and no inferential analysis is performed, or the category may be pooled with another category if this is justifiable from a scientific perspective.

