Considering the potential differences in patient populations, subgroup analyses by demographic and baseline conditions will be carried out to assess any potential impact of these differences on the results (see [Section 9.3.3](#)).

For study 1245.25, LLA-related events were not pre-specified in the protocol or specifically captured on eCRF pages (see [Section 9.3.2.1](#)). Therefore, the extent of reporting may be different from studies 1245.110 and 1245.121. As details on LLA events collected in studies 1245.110 and 1245.121 (the reasons leading to LLA, the number of LLA episodes, level of LLA, etc.) are not available in 1245.25, SAF-M2 is created for the purpose of analysing these specific details.

Although approx. 14 000 patients are expected to be included in this meta-analysis (see [Section 9.5](#)), the number of studies involved is low ( $N=3$ ). The 3 studies were designed to investigate empagliflozin's effect on cardiovascular events, and not specifically designed or powered to investigate LLA events. As all 3 studies are event-driven, duration of treatment and observation will be different for each patient, which will be taken into account using "time at risk" to adjust the incidence of outcomes (see [Section 9.3.1](#)). As all 3 studies investigate patients who meet the specific study entry criteria, the patients in this meta-analysis may not exactly reflect the circumstances in which empagliflozin is used in the routine clinical practice, thereby limiting the generalisability of the results.

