4.3 PLANNED ANALYSES

The following sections describe in detail the statistical analyses planned for disposition, demographic, and baseline characteristics considerations as well as the analyses planned for the safety endpoints described in [Section 4.1](#).

Meta-analysis methods

The meta-analysis will be performed in an exploratory manner. For the main outcomes (time to first LLA and time to first AE related to amputation), a Cox proportional hazards regression model for modelling the time to first event will be used, including the factors study, DM status (T1DM, T2DM, no diabetes) and treatment (all empa vs placebo). Study is assumed as a fixed effect in this meta-analysis.

Frequency analyses

For frequency analyses based on pooled data the estimates for the relative frequency is defined as follows:

$$\hat{p}_j = \frac{\sum_{i=1}^k w_{ji} \cdot \hat{p}_{ji}}{\sum_{i=1}^k w_{ji}}, \text{ where}$$

p_{ji} relative frequency in treatment group j and study (i=1,.., k)

$$w_{ji} = \frac{n_{ji}}{\sum_i n_{ji}}$$

denotes the weight of study i , $i=1, \dots, k$ in treatment group j

n_{ji} number of patients in treatment group j and study i ($i=1, \dots, k$)

Incidence rates

The frequency (%) of AEs does not take into account the duration of treatment. This is particularly important when studies with different treatment durations are pooled for analysis. In this case incidence rates may provide more accurate comparisons among groups.

Incidence rate is the number of new cases of an event occurring in a specified time period divided by the cumulative time at risk. The derivation of time at risk and incidence rates is as follows:

Patients with event:

time at risk in days = date of start of first event – treatment start date + 1

Patients without event:

time at risk in days = last date on treatment + 7 days*(or last date in study for secondary analysis based on ITT approach) – treatment start date + 1

* This is according to the definition of the residual effect period of 7 days as defined in the trial protocols for safety analyses for treatment emergent events.

The incidence rate per 100 patient years can then be calculated as follows:

Incidence rate [1/100 pt-yrs] = 100 * number of patients with event / sum of time at risk over all patients [years].

The estimate for a pooled incidence rate in treatment group j is defined as follows:

$$\widehat{IR}_j = \frac{\sum_{i=1}^k w_{ji} \cdot \widehat{IR}_{ji}}{\sum_{i=1}^k w_{ji}}, \text{ where}$$

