\widehat{IR}_{ji} Incidence rate in treatment group j and study ($i=1, \dots, k$)

$$w_{ji} = \frac{t_{ji}}{\sum_i t_{ji}}$$

denotes the weight of study i , $i=1, \dots, k$ in treatment group j

$w_{ji} = \frac{t_{ji}}{\sum_i t_{ji}}$ denotes the weight of study i , $i=1, \dots, k$ in treatment group j

t_{ji} sum of time at risk in treatment group j and study i ($i=1, \dots, k$)

The incidence rates will be calculated with two types of time at risk calculations.

The main analysis is the on-treatment approach where patients are censored at the date of treatment stop + 7 days and the secondary analysis is the ITT analysis where patients are censored at the last day of follow-up if no event occurred.

Time to event analyses

Kaplan Meier (KM) methods of cumulative incidence functions will be performed for time to event data (time to first event).

For pooled data across studies the cumulative incidence functions will be shown overall and stratified by study. The main analysis will be performed with censoring at the date of last study medication intake + 7 days for patients without event. An additional analysis will be performed whereby patients with no events will be censored at the date of last follow-up.

Cox proportional hazards models for modelling time to first event will be applied using factors study, DM status (T1DM, T2DM, no diabetes) and treatment (all empa vs placebo). For treatment comparison, hazard ratios with corresponding 95% confidence intervals as well as corresponding p-values will be presented.

The proportional hazards assumption will be explored by plotting $\log(-\log(\text{survival function}))$ against the log of time by treatment group and checked for parallelism. The interaction of treatment with log of time will be included in the model described above for an exploratory analysis. Further, Schoenfeld residuals for each covariate and treatment will be plotted against time and $\log(\text{time})$.

Competing risk analyses for time to event endpoints

Death is a competing risk for lower limb amputations. A competing risk analysis using a regression model by Fine and Gray (1999) [1] for amputations considering death as a competing event will therefore be performed. The regression model will include the following co-variables: study, diabetes mellitus (T1DM, T2DM, no diabetes), and treatment (empa vs. placebo).

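### The pooled Cox and Fine-Gray models leave out amputation predictors that are already planned baseline variables, so the HR is slightly attenuated and some power is lost (minor)

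*Protocol*

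**What the plan says.** Protocol 9.7.1 sets the main model: "Cox proportional hazards models will include the factors study, diabetes mellitus status (T1DM, T2DM, no diabetes), and treatment (all empa vs placebo"). SAP 4.3 agrees, under meta-analysis methods ("including the factors study, DM status (T1DM, T2DM, no diabetes) and treatment (all empa vs placebo") and under time to event analyses ("Cox proportional hazards models for modelling time to first event will be applied using factors study, DM status"). The competing-risk regression for LLA uses the same factors (Protocol 9.7.2.1; SAP 4.3). Protocol Table 9.7: 2 and SAP Table 4.3: 1 plan it for SAF-M1 only.

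Protocol 9.3.3 is headed Covariates. It names age, sex, renal function and insulin use, and also "peripheral arterial occlusive disease, diabetic foot, coronary artery disease, diabetic neuropathy, diabetic retinopathy, history of lower-limb amputation". Their stated use is that they "will be investigated in subgroup analyses of the LLA events and AEs related to amputation". The subgroup Cox model contains "study, treatment, <subgroup>, treatment-by-<subgroup> interaction" (Protocol 9.7.2.3; SAP 4.3.2.3 is equivalent), so it takes one variable at a time and drops diabetes status.

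No model with several baseline predictors is planned as a main, secondary or sensitivity analysis, and no reason is given for the choice of factors. For the treatment comparison, "hazard ratios with corresponding 95% CIs as well as corresponding p-values will be presented". The analysis is exploratory, and Protocol 9.9 says that the three studies were "not specifically designed or powered to investigate LLA events".

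**The concern.** PAOD, renal function and insulin use are plausible strong predictors of amputation. When a strong predictor is left out of a Cox model, the treatment HR is attenuated towards 1, even in a randomised comparison. In a safety analysis prompted by a class signal, that is the unfavourable direction. Chance imbalance in the predictors also stays in the estimate. The baseline tables will show it, but nothing removes it.

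The gap is widest in 1245.25. All its patients have T2DM (Protocol 9.2.2.1), so study and diabetes status are both constant there. Its own Cox model reduces to treatment alone. In SAF-M1, 7020 of 13 996 patients (50%) get no prognostic adjustment within their study.

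**Working it through.** **The plan's own figure.** 7020 + 4126 + 2850 = 13 996, which agrees with the stated approx. 14 000 (Protocol 9.1, 9.5). Empagliflozin: 2345 + 2342 + 2063 + 1425 = 8175, a share of 8175/13 996 = 0.584. The plan has no LLA event count, rate or power calculation to reproduce.

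**What sets the width of the interval.** Approximately, SE(log HR) = 1/√(d·a·(1−a)), with d the number of patients with events and a = 0.584. For d = 100, 200, 300 and 400 (assumed) the SE is 0.203, 0.143, 0.117 and 0.101. The 95% CI then multiplies and divides the HR by 1.49, 1.32, 1.26 and 1.22. Baseline covariates change neither d nor a, so adjustment should not narrow the interval.

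**Expected-count Cox fit, planned against adjusted.** Arm sizes are 4687/2333 in 1245.25 and 3488/3488 in the two heart failure studies together. Assumed for LLA: 0.4 to 1.0 events per 100 patient-years; PAOD 20%, HR 4; male sex 70%, HR 2; insulin 40%, HR 2; eGFR below 60 in 30%, HR 1.5.

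- A true HR of 1.97 (the canagliflozin figure in Protocol 7) is read as 1.95 to 1.96 by the planned model.
- The squared-z ratio, (z adjusted / z planned)², is 1.01 to 1.035, and under 1.02 if the predictors are weak.
- Check: with equal SEs the ratio is the squared ratio of log HRs. (ln 1.97/ln 1.95)² = 1.03 and (ln 1.97/ln 1.96)² = 1.02, in line with that range.
- For related AEs at an assumed 5 to 12 per 100 patient-years and predictor effects weaker than those for LLA, the ratio is about 1.02 to 1.10. That is worth roughly 2 to 10% more events.

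**Simulation on the documents' arm sizes.** The planned model was compared with the same model plus PAOD, prior LLA and neuropathy. Assumed: PAOD 20% in 1245.25 and 10% elsewhere; prior LLA 6% with PAOD and 1% without; neuropathy 30% with diabetes and 5% without; half of the heart failure patients diabetic; diabetes HR 3; follow-up of 1 to 4 years in 1245.25 and 0.5 to 3 years elsewhere. There were 500 runs per LLA row and 250 per related-AE row. Power is two-sided at 0.05 (assumed).

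| Outcome, true HR | Predictor HRs | Events | SE, planned / adjusted | Mean log HR, planned / adjusted | Power, planned / adjusted |
|---|---|---|---|---|---|
| LLA, 1.5 | 4, 5, 3 | 131 | 0.1974 / 0.1976 | 0.416 / 0.419 | 55% / 56% |
| LLA, 1.5 | 4, 5, 3 | 260 | 0.1389 / 0.1390 | 0.400 / 0.414 | 81% / 84% |
| LLA, 1.5 | 4, 5, 3 | 389 | 0.1133 / 0.1134 | 0.399 / 0.413 | 95% / 96% |
| LLA, 1.5 | 8, 10, 4 | 256 | 0.1399 / 0.1402 | 0.379 / 0.417 | 80% / 87% |
| Related AEs, 1.1 | 3, 4, 2 | 3653 | 0.0347 / 0.0348 | 0.086 / 0.093 | 69% / 74% |
| Related AEs, 1.1 | 6, 8, 3 | 3634 | 0.0348 / 0.0348 | 0.075 / 0.093 | 56% / 75% |

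The ratio of CI widths on the log scale is 1.000 to 1.002 throughout. With a true HR of 1.0 and 200 LLA events, both models rejected in about 4% of runs. Mean z rose by 1 to 4% in the first three LLA rows (squared, about 1.02 to 1.07) and by 10% in the fourth (1.21). For related AEs it rose by 8% (1.08² = 1.17) and 24% (1.24² = 1.54). Monte Carlo error on power is about 2 points for LLA and 3 for related AEs, with both models fitted to the same data.

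**The case against.** The strongest reply is that the main comparison needs no repair. Patients are randomised, study and diabetes status are in the model, everything is exploratory, and under no effect the planned model holds its error rate. For LLA the shift is 0.01 to 0.02 on an HR of 1.97, beside a cited interval of 1.41 to 2.75. The subgroup models show the treatment effect by PAOD, age, sex, eGFR and insulin use where events allow. All of this stands, and it is why the point is minor. The subgroup models do not answer it, because none gives an overall HR adjusted for several predictors.

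A reader might infer more than the documents support:

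- *That the plan gives up precision.* It does not, because the SE of the log HR is unchanged. The rise in z comes from a log HR further from zero, which belongs to a conditional HR.
- *That attenuation could hide an amputation signal.* The direction is unfavourable, but for LLA the size is far below sampling error. Even at 400 events the CI factor is 1.22, against 1.97/1.95 = 1.01.
- *That on-treatment censoring makes adjustment necessary.* Drug stop may depend on the same characteristics, but no size can be put on this, and an ITT analysis of both outcomes is planned.

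Three practical objections shape the fix. If pooled and single-study HRs were adjusted differently, the planned forest plot would mix two quantities. Missing covariates need a rule. Dedicated capture of LLA history is described only for 1245.110 and 1245.121 (Protocol 9.3.2.1), which is a reason to leave prior LLA off the list.

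**Conclusion.** The point holds as a minor one. The pooled models omit planned baseline predictors. The cost is slight attenuation and some power, with no loss of interval width and no loss of validity. It is very small for LLA (squared-z ratio 1.01 to 1.035; HR 1.97 read as about 1.95 to 1.96) and modest for AEs related to amputation (about 1.02 to 1.10 with moderate predictors).

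Every size rests on assumed event rates, prevalences and predictor effects. Stronger effects give larger figures, as the simulation shows, most clearly for the common secondary outcome. Whether these variables predict that outcome so strongly is uncertain. Its term list (SAP Appendix 6.1) also holds items such as dehydration, paraesthesia and skin infection.

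**What to change.** In Protocol 9.7/9.7.1 and SAP 4.3, pre-specify for SAF-M1 and SAF-M2 a Cox model for both outcomes with study, diabetes status, treatment and baseline PAOD, age, sex, eGFR and insulin use. Make the same additions to the Fine-Gray model for LLA where it is planned (SAF-M1). Fix the coding of age and eGFR and code patients without diabetes as not using insulin, since the subgroup table limits that variable to diabetic patients. Add a simple rule for missing covariates.

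State that the model estimates a conditional HR, and report it beside the three-factor model. Keep the three-factor model for the single studies and for the forest plot, so that study and pooled HRs remain comparable.

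The covariate list should be fixed before the 1245.121 and 1245.110 database locks (expected Q3 2020 and Q3 2021), because the 1245.25 amputations have already been reviewed.

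The cost is a wording change in both documents and a few more parameters in the pooled models. The added HR is conditional rather than more nearly marginal. No new data are needed.

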### **9.7.2 Further analysis**

#### **9.7.2.1 Further analyses of LLA events, AEs related to amputation, and details on LLA events**

##### *LLA events*

Subgroups by demographics, baseline medical conditions, and baseline therapies will be analysed for LLA events for SAF-M1 and SAF-M2 (see [Section 9.3.3](#) for subgroup variables and categorisation and [Section 9.7.2.3](#)).

An ITT approach will be used as a secondary analysis, which includes all events during the observation period after starting randomised treatment, regardless if the patient was taking study medication or not when the event occurred.

Since deaths are competing events to amputations, a competing risk analysis considering all-cause mortality and a cumulative incidence analysis will be carried out. The regression model will include the following co-variables: study, diabetes mellitus status (T1DM, T2DM, no diabetes), and treatment (all empa vs. placebo). Cumulative incidence for amputations and the competing events of deaths will also be displayed graphically.

The number of LLA episodes per patient will be summarised in a frequency table.

A listing of patients with recurrent events will be provided. Descriptive statistics (frequency tables with absolute and relative frequencies) will be provided to summarise all amputation events occurring after the first LLA event.

##### *AEs related to amputation*

Subgroup analyses for SAF-M1 and SAF-M2 will be carried out.

For AEs related to amputation, analyses for different grouped events will be performed (see the SAP [[c16853237](#), Appendix 6.1]). Cumulative proportions of patients and the number of patients at risk will be provided. In addition, Cox regression analyses will be performed for vascular AEs, diabetic-foot-related AEs, wound/infection, nervous system disorders, and

volume depletion events if the sample size is statistically sufficient, i.e. at least 14 patients with events in total over the 2 treatment groups have been reported.

An ITT approach will be used as a secondary analysis, which includes all events during the observation period after starting randomised treatment, regardless if the patient was taking study medication or not when the event occurred.

A listing of AEs with onset during any treatment other than the randomised treatment will be provided.

Additionally, AEs related to amputation preceding the amputation will be summarised for patients with amputation; AEs with onset after the amputation will not be considered in the analysis of this sub-population.

AEs related to amputations occurring after the first amputation event will be summarised using descriptive statistics (frequency tables with absolute and relative frequencies).

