## **8. RESEARCH QUESTION AND OBJECTIVES**

The primary objective of this exploratory meta-analysis is to evaluate the frequencies, incidence rates, and hazard ratios of lower-limb amputation (LLA) events (primary outcome) and of AEs related to amputation (secondary outcome) in patients treated with empagliflozin compared with placebo in the pooled population of the long-term studies 1245.25, 1245.110, and 1245.121 (SAF-M1), in the pooled population of studies 1245.110 and 1245.121 (SAF-M2), and in each of the 3 studies separately.

The exploratory objectives are to evaluate the frequencies of recurrent LLA events and of AEs related to recurrent LLA events and to assess the frequencies and incidence rates of patients with AEs related to amputation preceding the amputation for empagliflozin compared with placebo in SAF-M1, SAF-M2, and in each of the 3 studies separately. Further exploratory objectives are to evaluate the frequencies, incidence rates, and hazard ratios of the primary and secondary outcomes by subgroup and of the secondary outcome by grouped PTs for SAF-M1 and SAF-M2 as well as to assess details on LLA events for SAF-M2 in patients treated with empagliflozin compared with placebo.

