### **9.1 STUDY DESIGN**

This is a meta-analysis of 3 studies (1245.25, 1245.110, and 1245.121), which are randomised, placebo-controlled, double-blind, parallel-group, and event-driven studies. A meta-analysis of the 3 studies is considered appropriate to explore the risk for LLA events due to the large study size (approx. 14 000 patients in total in the 3 studies) and long-term exposure (median treatment exposure was 2.6 years in 1245.25; treatment exposure of up to 3 years are expected in ongoing studies 1245.110 and 1245.121). Data from individual patients from the 3 studies, not the result estimates of the 3 studies, will be pooled in the meta-analysis.

[figure not shown]
Study 1245.25 has been completed and the CTR is available [[c02695839](#)]. The study title is “A Phase III, multicentre, international, randomised, parallel group, double blind cardiovascular safety study of BI 10773 (10 mg and 25 mg administered orally once daily) compared to usual care in type 2 diabetes mellitus patients with increased cardiovascular risk”.

Study 1245.110 and 1245.121 are ongoing and the CTPs are available [[c03946327](#), [c09098452](#)]. The study title of 1245.110 is “A phase III randomised, double-blind trial to evaluate efficacy and safety of once daily empagliflozin 10 mg compared to placebo, in patients with chronic heart failure with preserved ejection fraction”. The study title of 1245.121 is “A phase III randomised, double-blind trial to evaluate efficacy and safety of once daily empagliflozin 10 mg compared to placebo, in patients with chronic heart failure with reduced ejection fraction”.

The overall designs of the studies are shown in [Figure 9.1: 1](#).

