### **9.3.1      Exposures**

Exposure is defined as the time exposed to study medication (on-treatment approach; calculated as the difference between the date of last intake of study medication and the date of the first administration of the study medication plus 1 day) or the time under observation after starting randomised treatment (ITT approach; calculated as the difference between the date of last follow up and the date of the first administration of the study medication plus 1 day; also see SAP [[c16853237](#), Section 4.3.2.1]).

For incidence rate, the derivation of time at risk is as follows:

Patients with event:

time at risk in days = date of start of first event – treatment start date + 1

Patients without event:

time at risk in days = last date on treatment + 7 days\* (or last date in study for secondary analysis based on ITT approach) – treatment start date + 1

\* This is according to the definition of the residual effect period of 7 days as defined in the trial protocols for safety analyses for treatment-emergent events (also see SAP [[c16853237](#), Section 4.3].

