### **9.3.2      Outcomes**

The objective of the meta-analysis is to evaluate the risk for LLA in an exploratory manner.

All outcome data, including recurrent events, are collected over the full trial period even after the first amputation event.

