Disposition, demographics, exposure	Yes	Yes	Yes	Yes	Yes
Concomitant diagnoses and therapies	Yes	Yes	Yes	Yes	Yes
Lower limb amputation					
Frequencies	Yes	Yes	Yes	Yes	Yes
Incidence rates	Yes	Yes	Yes	Yes	Yes
Time to onset analyses	Yes	Yes	Yes	Yes	Yes
Time to onset analyses with competing risk	Yes	-	-	-	-
Sensitivity analyses (heterogeneity analyses, forest plot)	Yes	Yes	-	-	-
Adverse events related to amputations (definition based on list of PTs)					
All patients					
Frequencies	Yes	Yes	Yes	Yes	Yes
Incidence rates	Yes	Yes	Yes	Yes	Yes
Time to onset analyses	Yes	Yes	Yes	Yes	Yes
Patients with amputations only, i.e. preceding events					
Frequencies	Yes	Yes	Yes	Yes	Yes
Incidence rates	Yes	Yes	Yes	Yes	Yes
Time to onset analyses (KM only)	Yes	Yes	Yes	Yes	Yes
Lower limb amputation events occurring after the first LLA event					
Descriptive Statistics (Frequency tables with absolute and relative frequencies)	Yes	Yes	Yes	Yes	Yes
Adverse Events related to amputations occurring after the first LLA event					
Descriptive Statistics (Frequency tables with absolute and relative frequencies)	Yes	Yes	Yes	Yes	Yes

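### Incidence rates of AEs preceding amputation: applied as written, time at risk runs past the first LLA, after which no AE counts, so rates are too low whenever amputees without a preceding AE have later time

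*Protocol*

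**What the plan says.** Protocol Section 8 lists as an exploratory objective "to assess the frequencies and incidence rates of patients with AEs related to amputation preceding the amputation for empagliflozin compared with placebo". Protocol Table 9.7: 2 and SAP Table 4.3: 1 carry this as a separate block, "Patients with amputations only, i.e. preceding events", with incidence rates marked Yes for both pools and all three studies. SAP 4.3.2.2.2 adds that preceding events are tabulated by PT group, SOC and PT, with incidence rates shown as well.

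The numerator closes at the amputation. Protocol 9.7.2.1 states that "AEs with onset after the amputation will not be considered in the analysis of this sub-population", and SAP 4.3.2.2.2 likewise leaves out events after the first amputation.

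The denominator is set by general rules in Protocol 9.3.1, repeated in SAP 4.3. A patient with an event contributes time up to the first event. For a patient without one, the on-treatment rule is "time at risk in days = last date on treatment + 7 days", less the treatment start date, plus 1; the alternative end point is "or last date in study for secondary analysis based on ITT approach". The SAP confirms that "The incidence rates will be calculated with two types of time at risk calculations", namely these two. Neither document gives a rule specific to amputees. Protocol 9.3.2 adds that "All outcome data, including recurrent events, are collected over the full trial period even after the first amputation event", so observation continues past the LLA.

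**The concern.** Both documents define an incidence rate as new cases divided by cumulative time at risk. In this sub-population a patient stops being at risk of a countable event at the first LLA. Under the stated rules, though, an amputee without a preceding AE keeps adding person-time until last treatment plus 7 days or the end of the study. That time can only enlarge the denominator, so the rate can only fall.

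At stake is the accuracy of a descriptive rate that the plan names as an objective, and of its comparison between empagliflozin and placebo. What happens after the amputation (how long patients stay on drug or in study) would enter a measure meant to describe what came before it.

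**Working it through.** The documents give no rate for this sub-population, so there is no figure to reproduce. The check applies the plan's own formula under both end points.

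**Formula.** Rate = 100 × patients with event / total time at risk in years. With a share p of amputees having a preceding AE, mean person-time per amputee is:
- ending at LLA: p × E[AE time] + (1 − p) × E[LLA time]
- as written: p × E[AE time] + (1 − p) × E[end of time at risk]

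Shortfall = 1 − (first / second).

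**Hand example.** Ten amputees, LLA at 1.0 year, last date in study at 2.6 years, seven with an AE at 0.75 year.
- Ending at LLA: 7 × 0.75 + 3 × 1.0 = 8.25 years; 100 × 7/8.25 = 84.8 per 100 patient-years.
- As written (ITT): 7 × 0.75 + 3 × 2.6 = 13.05 years; 100 × 7/13.05 = 53.6, which is 37% too low.

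**Inputs for the general case.** From the documents: 2.6 years, since "median treatment exposure was 2.6 years in 1245.25" (Protocol 9.1). It is an all-patient median in one study, used here as common follow-up for every amputee. Assumed: LLA uniform over those 2.6 years; AE onset uniform within the last w = 3, 6 or 12 months before LLA; the share p; the fraction stopping drug at LLA.

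**One case in full (w = 0.5 year, p = 70%, nobody stops).** E[LLA] = 1.3. E[AE time] = 1.3 − (0.5 − 0.5²/5.2)/2 = 1.074. End as written = 2.6 + 7/365.25 = 2.619.
- Ending at LLA: 0.7 × 1.074 + 0.3 × 1.3 = 1.142; rate 61.3.
- As written: 0.7 × 1.074 + 0.3 × 2.619 = 1.538; rate 45.5; shortfall 26%.

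**Shortfall over w = 3 to 12 months:**

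| Share with preceding AE | Nobody stops drug at LLA (also ITT) | Half stop, on-treatment |
|---|---|---|
| 95% | 5.2-6.7% | 2.7-3.5% |
| 70% | 24.3-28.0% | 14.2-16.5% |
| 30% | 41.9-43.9% | 27.0-28.4% |

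If all stop drug at LLA, only the 7 extra days remain and the on-treatment shortfall is at most 1.4%. The ITT rate does not benefit: its time at risk still runs to the last date in study. At p = 100% there is no shortfall. Using 3.0 years instead of 2.6 changes these figures by less than 1 percentage point.

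**Arm comparison, different shares (w = 0.5 year).** With 70% against 50% having the AE, rates ending at LLA are 61.3 and 42.1, ratio 1.46. As written with nobody stopping they are 45.5 and 27.1, ratio 1.68; with half stopping, 1.59; with all stopping, 1.46 on-treatment.

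**Arm comparison, same share and same time after LLA.** Both arms have 70% with the AE, onset 0.25 year before LLA, and 1 year of time at risk after LLA; LLA falls at 1 year in one arm and 2 years in the other.
- Ending at LLA: 0.7/(0.7 × 0.75 + 0.3 × 1) = 84.8 per 100 and 0.7/(0.7 × 1.75 + 0.3 × 2) = 38.4 per 100; ratio 2.21.
- As written: 0.7/(0.7 × 0.75 + 0.3 × 2) = 62.2 and 0.7/(0.7 × 1.75 + 0.3 × 3) = 32.9; ratio 1.89.

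Matching the share and the post-LLA time is therefore not enough to protect the ratio; the timing of the AE and LLA matters too.

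**The case against.** The best counter-argument is that restricting the sub-population analysis to events before the amputation already implies that observation ends there, and that a sensible programmer would cut time at risk at the LLA. The documents do not say so. The restriction is worded for events, the time-at-risk rules are general, and the SAP names exactly two end points. The argument does, however, limit the claim to what follows if the rules are applied as written.

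The effect is also conditional. It disappears in a category where every amputee has a preceding AE. On-treatment, it is almost absent if drug stops at LLA, and an amputee who stopped more than 7 days before the LLA adds no later time. SAP Appendix 6.2 describes amputation as a procedure performed for an AE, and the PT list includes gangrene, osteomyelitis, diabetic foot and peripheral ischaemia, so a high share is plausible for the overall category. The large shortfalls belong mainly to single PT groups or PTs, which the SAP also tabulates.

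The stakes are modest: this is a descriptive rate in an exploratory study, in a subset selected by an event after randomisation. Even with the right denominator the rate ratio between arms is not a randomised comparison.

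A reader might infer that the Kaplan-Meier curves planned for the same patients are wrong in the same way. That does not follow. Keeping amputees without a preceding AE in the risk set gives a cumulative-incidence type of curve with LLA as the terminating event, so censoring at LLA there is a debatable choice. A reader might also infer that hazard ratios are biased, but the analysis tables allow only Kaplan-Meier, not Cox, for time to onset in this block.

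**Conclusion.** The point holds for the incidence rates of preceding AEs in amputees, and for nothing wider. The numerator closes at the first LLA and the stated denominator does not, so the rate is too low whenever amputees without a preceding AE have time on drug (or, for ITT, in study) after the LLA. The direction follows from the formula; the size rests on the assumptions listed above and cannot be taken from the documents. The ratio between arms is generally distorted if the arms differ in the share with a preceding AE, in time after LLA, or in time to AE or LLA. Frequencies, the all-patient AE analyses, hazard ratios and the primary LLA analysis are unaffected. The correction should be made, but no main conclusion depends on it.

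**What to change.** In Protocol 9.3.1 and SAP 4.3, add one sentence: for incidence rates in patients with amputations only (preceding events), time at risk for patients without a preceding AE = min(date of first LLA, last dose + 7 days or, for ITT, last date in study) − treatment start date + 1. The rule for patients with a preceding AE stays as it is.

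The cost is one sentence in each document. No new data are needed: LLA dates are recorded on the eCRF in 1245.110 and 1245.121, and were retrieved or imputed for 1245.25 (Protocol 9.7.3.1, SAP 4.2 and Appendix 6.2).
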